PROTOCOL TITLE: Broadening the Reach, Impact, and Delivery of Genetic Services (BRIDGE)

NCT NUMBER: NCT03985852

PROTOCOL DATE: 06/05/2019

The full trial protocol is available at:

[name], [name], [name], et al. Comparing models of delivery for cancer genetic services among patients receiving primary care who meet criteria for genetic evaluation in two healthcare systems: BRIDGE randomized controlled trial. *BMC Health Sciences Research*. 2021;21:542. doi:10.1186/s12913-021-06489-y

Date: Tuesday, August 6, 2024 10:49:19 AM

[Print](#)[Close](#)**IRB_00123563****Created:** 6/5/2019 3:01 PM**PI:** [name]**Submitted:** 3/5/2019**Title:** Broadening the Reach, Impact, and Delivery of Genetic Services**IRB_00123563**

1. Contacts and Title

1. Study Introduction

1. Responsible Investigator:

[name]

Email	Training	Col Date
[contact]	4/25/2022 SMCG	3/19/2024

a. Position of the Investigator:

Faculty or Non-Academic Equivalent

Student

Staff

Resident/Fellow

Other

2. Contact Persons for the Responsible Investigator:

Name	Email	Training
[name]	[contact]	2/22/2023 MCG
[name]	[contact]	3/4/2024 SMCG
[name]	[contact]	3/21/2022 SMCG
[name]	[contact]	1/9/2023 SMCG

3. Guests of the Responsible Investigator:

Last Name	First Name	E-Mail
[name]	[contact]
[name]	[contact]
[name]	[contact]
[name]	[contact]
[name]	[contact]

4. What type of application is being submitted?

New Study Application (or Amendment/Continuing Review)

5. Title Of Study:

Broadening the Reach, Impact, and Delivery of Genetic Services

6. Study Purposes and Objectives:

The proposed study will employ an implementation science framework to compare two models of genetic services delivery for 1,920 patients in a randomized controlled trial with clinic-level randomization. We hypothesize that uptake of genetic testing (Study Aim 2) and adherence to management recommendations (Study Aim 3) will be equivalent between the genetic services delivery models. We propose the following Specific Aims:

Aim 1) Identify primary care patients who qualify for genetic risk assessment in two healthcare systems using a CDS infrastructure to automatically evaluate family history.

*This aim has already been studied in IRB #105797. We will be utilizing this tool that is now available. Aim 1 will not be analyzed in this protocol but is part of our overall research model.

Research Aims to be studied in this protocol:

Aim 2) Compare uptake of genetic testing for patient-directed standard of care vs. enhanced standard of care genetic services delivery models for 1,920 unaffected primary care patients. We will utilize a randomized trial design with clinic-level randomization to compare two standard of care models: a *patient-directed standard of care* model and an *enhanced* model. In the *patient-directed* model those identified by the clinical decision support (CDS) infrastructure as meeting testing criteria will be informed of their cancer risks, provided with educational resources, and offered the option to select genetic testing through a patient portal. This online portal will be overseen by HCI genetic counselors. The *enhanced standard of care* model in which primary care providers and patients are notified through CDS when criteria are met (the *enhancement* of standard of care) and of the availability of standard of care genetic services. We will compare uptake of genetic testing by model and by race/ethnicity and rurality.

Aim 3) Compare adherence to recommendations and other patient responses for the genetic services delivery models. We will compare the effects of the genetic services delivery models on adherence to management recommendations at 12 months after return of results, or last genetic services contact. We will assess cognitive (i.e., recall, comprehension, uncertainty, risk perceptions) and affective (i.e., test-related distress, positive reactions, decision regret) responses at 4 weeks, and communication (i.e., family, provider) interactions at 4 weeks and 12 months after last genetic services contact. We will also examine differences in effects by race/ethnicity and rurality.

7. Is this a multi-site study, where more than one site needs IRB approval?

Yes No

8. Background and Introduction:

Identifying unaffected individuals with inherited cancer susceptibility is critical to risk reduction and clinical management. Hereditary cancer syndromes affect risks of many common, adult-onset cancers.¹⁻⁵ Pathogenic variants (i.e., variant that increases cancer risk; PVs) in cancer predisposition genes can be identified in 7% of breast, 11%-15% of ovarian,^{2,6-8} 10% of colorectal,^{3,9,10} 4%-11% of pancreas,¹¹ and 12% of advanced prostate cancers.^{12,13} Prior evidence supports individualizing screening and prevention based on cancer risk,¹⁴⁻¹⁹ such as more frequent or earlier screening or chemoprevention, and identification of a PV may allow for targeted intervention and treatment if cancer occurs.²⁰⁻²³

Advances in technology are identifying more families with an inherited cancer susceptibility. Next generation sequencing-based testing of panels of multiple genes for hereditary cancer (i.e., multigene panel) can more than double the rate of mutation detection compared to testing single genes.²⁴⁻²⁷ A growing number of genes have been associated with increased risks for breast, ovarian, pancreas, and prostate cancers^{7,11,13,28-30} and multiple genes, in addition to Lynch syndrome, have been identified in association with colorectal cancer risk.^{10,31,32} Newer sequencing technologies are also expanding the tumor spectrum associated with particular genes, leading to a broader range of family histories being considered as an indication for genetic testing. For example, family history of prostate and pancreas cancer are being incorporated into testing criteria for homologous DNA repair pathway genes (e.g., *BRCA1/2*), criteria that were previously restricted to only breast and ovarian cancer.³³ Healthcare systems are challenged by the clinical management of the increasing number of patients who qualify for these services.^{19,34}

There is a need to expand beyond cancer patient populations. Efforts to identify individuals with inherited cancer susceptibility are still generally focused on cancer patients with testing of at-risk relatives recommended once a PV is found.³⁵⁻³⁷ However, this strategy misses families in which there is no living, affected relative to test, and may be an important barrier to accessing genetic services. One report found that 50% of unaffected patients presenting for clinical genetic counseling who received a recommendation for a relative to be tested first were lost to follow-up.³⁸ Studies have begun to explore the feasibility of screening primary care patients for inherited cancer susceptibility.³⁹⁻⁴² National guidelines recommend testing for unaffected individuals with a significant family history,^{43,44} and the Affordable Care Act mandated coverage of genetic testing for hereditary breast/ovarian cancer for unaffected individuals with appropriate family history.⁴⁵ However, these initiatives have not yet been systematically implemented into primary care practice and it is unclear to what extent the need for genetic testing for hereditary cancer in unaffected individuals is being met. The National Health Interview Survey reported that only 9.5% of unaffected women with a family history of breast and ovarian cancer had discussed genetic testing with their healthcare provider, and only 2.7% had genetic testing.⁴⁶ Strategies to identify unaffected individuals across healthcare systems are therefore needed.

Family history can stratify patients' cancer risk but is underutilized in primary care. While debate continues over population-wide cancer genetic testing,⁴⁷⁻⁵⁰ this strategy has not yet been widely implemented outside of research contexts, and often only in specific populations.⁵¹⁻⁵⁴ Family history can be used effectively to identify those most likely to carry a PV and to tailor screening regardless of whether a PV is identified.⁵⁵⁻⁶¹ However, although some family history is generally collected in primary care, the information is underutilized to stratify risk,⁶²⁻⁶⁴ leading to missed prevention opportunities. In recent research, 37% of newly diagnosed breast cancer patients found to have PVs had a family history that warranted genetic testing even prior to their diagnosis.⁶⁵ Commonly reported

barriers to collection and use of family history information in clinical practice include limited visit time, competing demands, reimbursement criteria, and providers' training, knowledge and skills.^{63,66-70} To address these barriers, over 75 tools have been developed⁷¹⁻⁷⁶ for patients to collect their family history information prior to a clinic visit to improve discussions with primary care providers (PCPs).^{63,64,66,67,77-80} However, many of these tools require significant time and resources, were developed independent of workflow standards in clinics, and widespread implementation of these tools has not occurred.⁶⁴ Therefore, it is critical to develop novel strategies to capitalize on family history information already being collected in the EHR, regardless of the method, and pair it with automated tools for evaluation and stratification of risk.

Clinical decision support (CDS) tools and electronic health record (EHR) technology can utilize available family history information. System-level strategies have been suggested to assist PCPs in providing genetic services for patients.⁸¹ EHR technology, together with CDS tools, are promising as systematic approaches to address many of the PCP time, knowledge, and skills barriers that limit the use of available family history information. CDS entails providing providers and patients with pertinent knowledge and/or person-specific information, intelligently filtered or presented at appropriate times, to enhance health and healthcare.⁸² While CDS interventions have not always improved clinical care, we and others have identified best practices for optimizing effectiveness.^{83,84} In prior studies, CDS tools have increased the efficiency of a hereditary cancer service,⁸⁵ improved referral patterns for patients at high risk for familial cancers,⁸⁶ and enhanced identification of Lynch syndrome among newly diagnosed colon cancer patients.⁸⁷

Prior research comparing approaches for delivering cancer genetic services is limited. Once at-risk individuals are identified, genetic services (e.g., genetic counseling, genetic testing, risk-reduction recommendations) need to be delivered. The number of trained genetic specialists is limited with more sustainable approaches needed to accommodate an increasing patient volume.⁸⁸ Prior studies have compared mode of delivery (i.e., in-person vs. telephone) based on a traditional service model, with patient contact by a genetic counselor before and after genetic testing, examining outcomes such as uptake of genetic testing, adherence to follow-up, and patient responses (e.g., anxiety).⁸⁹⁻⁹¹ However, few studies have involved PCPs or explored supplementing genetic counselors with other models (i.e., computer-based pre-test education^{92,93}) within the healthcare system. Implementation research studies⁹⁴ are urgently needed to compare the outcomes in real-world settings of different models to genetic services delivery, particularly models that direct genetic counseling resources to those patients with the greatest needs for genetic services.

Potential of patient-directed models of genetic services delivery has not been explored. Genetic testing is now available direct-to-consumer (DTC), including testing with multi-gene cancer panels, with no or minimal involvement of a clinician or genetic counselor.⁹⁵ Advocates believe DTC approaches increase access to genetic testing, particularly for patients in areas with few genetic services. However, it is unknown whether DTC genetic testing will result in appropriate management.⁹⁶ Clinicians need to be aware of the results to incorporate them into care, but a study of early adopters found that only 27% of patients had shared DTC results with their PCPs.⁹⁷ In addition, PCPs may have limited knowledge about how to use the results to individualize care.⁹⁸ Healthcare systems have a vested interest in ensuring that information as significant as genetic testing be part of the EHR in a meaningful way.⁹⁹ Therefore, there is significant need to develop genetic services delivery strategies that incorporate features of the DTC approach (e.g., patient-directed, increased access) but within the healthcare system and with support for providers interpreting these results.

Need to address disparities in access and use of genetic services across population subgroups. Prior research has often shown that individuals from racial and ethnic minority groups have decreased access to and utilization of genetic services,¹⁰⁰ even when cost barriers are minimized.¹⁰¹ These disparities have been attributed to individual-level factors (e.g., awareness, knowledge, attitudes)¹⁰²⁻¹⁰⁴ and system-level factors (e.g., insurance, access to specialists, lower trust).^{103,105} One study with women diagnosed with breast cancer showed a strong desire for genetic testing among Latinas, but also that minority patients had more unmet needs for discussion of testing with providers.¹⁰⁶ Prior work has also indicated the importance of examining how race and ethnicity impact the delivery of genetic services. A randomized trial comparing in-person vs. telephone-based genetic counseling found that the effect of mode of delivery differed by race; minority women assigned to telephone counseling were the least likely to complete genetic testing.¹⁰⁷

Even less research has examined access and use of genetic services by rurality (rural/frontier vs. urban). Rurality is a critical issue for Utah; 96% of the landmass is defined as rural (<100 persons per square mile) and 70% as frontier (<7 persons per square mile).¹⁰⁸ Individuals in rural areas in the U.S. have less access to care¹⁰⁹ and worse health outcomes.^{110,111} Rural counties have higher incidence of cancers potentially preventable through screening.^{112,113} Some disparities in cancer mortality are likely due to barriers to accessing health services in rural areas.¹¹³ Clinical sites in rural areas may not have physicians knowledgeable about genetics.¹¹⁴ In addition, in rural/frontier regions, clinics and hospitals can be hundreds of miles from patients' homes, so rural/frontier residents have less access to specialty genetics care.^{70,115}

Citations can be found in the appropriate Documents & Attachments section.

IRB_00123563

Created: 6/5/2019 3:01 PM

IRB_00123563

2. Study Location and Sponsors

PI: [name]

Submitted: 3/5/2019

Title: Broadening the Reach, Impact, and Delivery of Genetic Services**2. Study Location and Sponsors**

1. Add all locations applying for approval of research via the University of Utah IRB or Human Research Protection Program (HRPP).

Click the appropriate button(s) below to add locations:

Site Name	Investigators Name	Covered Entity	Sub Sites

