Patients meeting National Comprehensive Cancer Network guidelines for referral for genetic services will be identified using the screening tool developed and implemented in the EPIC EHR (Study Aim 1). The primary care providers (PCPs) of eligible patients will be notified of their patient's eligibility one week prior to patients being notified of the recommendation for genetic services. Patients will then be referred to participate in standard of care genetic services, with the clinical procedures depending on the study arm to which the clinic was randomized: enhanced standard of care or patient-directed standard of care.

Patients meeting criteria will be notified of the recommendation through the patient portal (i.e. MyChart). Those who do not have MyChart will be notified by mail. Those notifications will be followed by standard scheduling procedures. Patients who do not have MyChart will be asked to sign up for MyChart when they are contacted. Those who were not actively using MyChart will be provided with a refresher on the use of MyChart since this project focuses on using this tool to deliver genetic services more effectively.

Patients who do not have access to the internet or are unwilling or able to use MyChart will be directed to in person genetic counseling services. A waiver of consent will be requested to track the individuals who are not able to participate through MyChart, but they will not be asked to complete study questionnaires.

Study Arms – Clinic Randomized

Enhanced Standard of Care

This arm is referred to as enhanced since clinical decision support (CDS) tools are used to identify patients meeting guidelines rather than relying solely on provider identification of patients. Patients in this arm will have an in-person or telephone pre-test genetic counseling visit. Pre-test counseling includes review of the family history, risk assessment, discussion of the purpose of genetic testing and possible outcomes, implications for insurance coverage, costs, and assessment of psychosocial needs.

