Patients can opt to proceed with genetic testing during this session. Consent for testing will be documented and a sample can be collected at that time or scheduled at another time that is convenient for the patient. All test results are returned by a genetic counselor by phone or in person based on patient preference per clinic protocol. A copy of the results and letter with tailored screening recommendations are returned to the PCP and patient via the patient portal (i.e. MyChart) or via a letter in the mail.

Patient-Directed Standard of Care

Patients in this arm will be offered genetic services through the patient portal (i.e. MyChart). These educational resources will present standard pre-test genetic counseling information as described in the Enhanced Standard of Care Arm. Patients who decide to proceed with genetic testing will be asked to document consent for testing.

Patients who decide to have genetic testing will have a saliva collection kit, instructions, and shipping materials sent to their homes to collect and return a sample to the testing laboratory; this is a service offered by commercial laboratories. Patients will have an opportunity to contact the genetics clinic with any questions or to request an appointment with a genetic counselor at any time.

All results will be reviewed by a genetic counselor. Negative results will be returned along with a letter including screening recommendations tailored based on family history to the patient and PCP via the patient portal. Genetic counselors will return results for pathogenic variants and variants of uncertain significance via phone. A copy of the results and letter with tailored screening recommendations will be provided to the patient and PCP via the patient portal.

All patients will be offered the option to schedule follow-up appointments in the genetics clinics; these contacts and appointments will be tracked.

Standard of Care Genetic Testing

Genetic testing will be performed at Clinical Laboratory Improvement Act (CLIA)-certified, commercial laboratories. Based on standard clinical practice, the choice of laboratory will be based on services provided and patient's insurance and/or financial status. Testing will be billed to insurance. Patients who are uninsured or lack coverage for genetic testing will be assisted in applying for aid through programs offered by the laboratories.

Genetic testing will not be required to participate in the research questionnaires.

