Research Procedures

1. A research coordinator or genetic counseling assistant will determine who is eligible to participate in the research procedures based on participation in genetic services and access to MyChart, the patient portal. A waiver of recruitment is being requested for this authorization. Up to 20,000 unique electronic health records may be accessed to determine inclusion in this study, and basic health outcomes tracked for comparison.
2. Consent cover letter will be sent via patient portal to offer participation in this research study, with a link to an online questionnaire. The consent cover letter will be sent to patients approximately 4 weeks after genetic test results are returned for those who decide to test and about 8 weeks after participation in pre-test genetic counseling services for those who decide not to test.

If no response is received to the first message, after 1 week another message in the patient portal will be sent. If still no response up to 3 phone calls will be made.

3. Online questionnaires will utilize REDCap, which has a HIPAA-compliant interface. Estimated 960 patients will be offered participation through University of Utah Health; 1,960 patients over both participating sites.

i. **Questionnaire #1:** At about **4 weeks after return of results for those who decide to test** (8 weeks after pre-test genetic counseling), we will assess cognitive (i.e., recall, comprehension, uncertainty, risk perceptions), affective (i.e., test-related distress, positive reactions, decision regret), communication (i.e., family, provider) responses, experience with genetic counseling, and sociodemographic characteristics including numeracy for those who decide to test. For those who do not decide to test, we will assess experience with genetic counseling, reason for not testing, decision regret, risk perceptions, and sociodemographic characteristics including numeracy.

ii. **Questionnaire #2:** At about **12 months**, we will ask about discussion of their test results with their PCP, family members, or others, and self-reported use of cancer screenings for those who decide to test. We will also utilize EHR data to examine adherence to recommendations. For those who decide not to receive genetic testing, we will assess the self-reported use of cancer screenings, whether genetic testing was pursued at another time or through another source, communication with family members and whether other relatives had testing.

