iii. After each returned questionnaire, participants will be compensated via the patient portal with a thank you message and a \$10 e-gift card. This totals \$20 dispersed if both questionnaires are returned.

iv. For any participants who would like to complete questionnaires by telephone, a genetic counseling assistant or research coordinator will administer the questionnaire. Calls will be digitally recorded to allow for analysis of comprehension. Each questionnaire will take about 15 minutes to complete. Participants may also complete the questionnaires by mail if they choose.

4. Study staff will track the EHR of participants who were identified by the CDS algorithms. Any screenings, care or health procedures related to genetic services will be recorded in the research record to determine if an impact is made because of participation in genetic services. This is estimated to be up to 20,000 individual records in the EHR.
5. Data analysis for outcome data will occur after patient enrollment is complete. Patients who return questionnaires will be compared to similar cohorts that were not directly involved with research questionnaires.

More specific details of data analysis are outlined in the statistical methods section.

7. Are all procedures for research purposes only (non-standard or non-standard of care procedures)?

Yes No

If no, list the procedures that are performed for research purposes only (non-standard or non-standard of care procedures):

Questionnaire #1: estimated 4-8 weeks from last genetic services contact (4 weeks for those who decide to test and 8 weeks for those who decide not to test)

Questionnaire #2: estimated 12-months from last genetic services contact

Data Analysis of genetic services impact and outcomes

8. Is there a safety monitoring plan for this study?

Yes No

9. Provide a summary of the statistical methods, data analysis, or data interpretation planned for this study. Factors for determining the proposed sample size (e.g., power) should be stated.

Research Aims Analysis for this specific IRB:

Aim 2 Analysis.

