Aim 3 analysis will follow analytic procedures to address the dimension of Effectiveness from our conceptual framework. For comprehension, concordance between patient responses and information from genetic counselors' notes will be scored. We will test bivariate relationships between the outcome variables and study arm using Student's t-test or the nonparametric Wilcoxon rank-sum test between continuous variables, and chi-square test (or Fisher's exact test if small cell counts) for categorical data. We will examine distributions for continuous outcomes and transform the data if skewed. Procedures for building multilevel multivariable linear (continuous outcomes) or logistic (binary outcomes) regression models are described above. Regression models extended to include random effects for clinic or provider will be fit using software for linear mixed models for continuous outcomes and generalized linear mixed models for categorical outcomes. As with Aim 2, we will examine effect modification by testing for significant interactions between variables in regression models.

Aim 3 Sample Size

We estimate a sample size of 1,100 for a multilevel multivariable regression analysis with >90% power to detect a small effect size (0.02) attributable to 2 independent variables using an F-Test with an alpha of 0.05 using PASS 15 Software. The variables tested are adjusted for an additional 20 independent variables. To examine effect modification sample size is calculated based on logistic regression of a binary response variable (Y) on a binary independent variable (X) and a binary confounder variable (Z) with a sample size of 1,710 observations achieves 80% power at a 0.05 significance level to detect the X-Z interaction odds ratio of 1.5. Calculations assume that a two-sided Wald test is used.

IRB_00123563

Created: 6/5/2019 3:01
PM

IRB_00123563

- Request for Waiver of Consent

PI: [name]

Submitted: 3/5/2019

Title: Broadening the Reach, Impact, and
Delivery of Genetic Services**Request for Waiver or Alteration of Consent***** Requested Waivers**

Date Created	Type of Request	Purpose of Waiver Request
View 3/18/2019	Waiver of Informed Consent	Waiver of consent for chart review without patient contact

IRB_00123563

Created: 6/5/2019 3:01 PM

PI: [name]

Submitted: 3/5/2019

IRB_00123563

IRB Smart Form

Title: Broadening the Reach, Impact, and Delivery of Genetic Services

Request for Waiver or Alteration of Consent

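### As defined, the Aim 3 adherence comparison is conditional on engagement after randomisation, and no analysis of all identified patients by allocated clinic is committed to

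*Combined protocol and SAP*

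**What the plan says.** The study purpose (section 1, item 6) hypothesises that "adherence to management recommendations (Study Aim 3) will be equivalent between the genetic services delivery models". Aim 3 in the same item promises to compare the effects of the models on "adherence to management recommendations at 12 months after return of results, or last genetic services contact". Clinics are randomised, with "clinical procedures depending on the study arm to which the clinic was randomized" (section 4, item 6, Patient Screening).

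The routes into services differ by design. In the enhanced arm, "Patients in this arm will have an in-person or telephone pre-test genetic counseling visit". In the patient-directed arm, services are offered through the portal. In both arms, tailored recommendation letters are described only as part of returning test results. For the patient-directed arm, for example, "Negative results will be returned along with a letter including screening recommendations tailored based on family history to the patient and PCP" via the portal.

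On data, Research Procedures 3.ii says "We will also utilize EHR data to examine adherence to recommendations". That sentence stands between one on testers and one on non-testers, who are asked about their use of screening. Research Procedures 4 adds that "Study staff will track the EHR of participants who were identified by the CDS algorithms", up to 20,000 records. The Aim 3 Analysis (section 4, item 9) says "We will test bivariate relationships between the outcome variables and study arm", followed by multilevel models. It names no analysis set, no rule for patients who never engage or test, and no equivalence margin.

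**The concern.** Randomisation protects a comparison of everyone identified at the allocated clinics. It does not protect a comparison of those who went on to use services or to test, because the model influences who they are. A patient with no services contact has neither of the stated starting points. A patient who declines testing has a starting point (last contact) but no described letter against which adherence could be scored. Read as written, the Aim 3 comparison therefore conditions on a consequence of allocation.

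What is at stake is the Aim 3 conclusion. A model that draws in additional, less adherent patients can look worse among users while producing more adherent patients overall. A real deficit can also be hidden by a favourable mix of users and reported as equivalence.

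**Working it through.** **The plan's own figure.** The Aim 3 sample size is 1,100, with more than 90% power for an effect size of 0.02, 2 tested variables, 20 covariates and alpha 0.05. A noncentral F calculation with df1 = 2, df2 = 1,100 − 23 = 1,077 and noncentrality 1,100 × 0.02 = 22 gives 99.1% before any allowance for clustering, so the statement holds. It is a test to detect a difference, not an equivalence calculation, and it does not say which patients make up the 1,100.

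**Illustrations.** The documents give no uptake or adherence rates, so every rate below is assumed.

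*Equal uptake, no true effect on any patient.* Let s be the share of each arm's users who would engage under either model. Let gap be the adherence difference between those who engage only under one model and those who engage only under the other. Then

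spurious difference among users = (1 − s) × gap.

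| s | gap (points) | spurious difference (points) |
|---|---|---|
| 0.90 | 20 | 2 |
| 0.75 | 20 | 5 |
| 0.50 | 20 | 10 |

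Equal uptake in Aim 2 would therefore not remove the problem, because equal rates can hide different people.

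*Masking.* Take a true deficit of 15 points, s = 0.50 and an opposing gap of 30 points: −15 + 0.50 × 30 = 0. The user comparison shows no difference.

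*Unequal uptake, no true effect.* Enhanced arm: 16% engage and 80% of them adhere. Patient-directed arm: the same 16% plus a further 10% who adhere at 50%.

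- Adherence among patient-directed users: (0.16 × 0.80 + 0.10 × 0.50) / 0.26 = 0.178 / 0.26 = 68.5%.
- Difference among users: 68.5 − 80 = −11.5 points.
- Adherent users per 100 identified patients: 12.8 v 17.8, the opposite direction.

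A smaller uptake gap still matters. With 16% v 20% and the extra users adhering at 40%, (0.128 + 0.016) / 0.20 = 72%, a difference of −8 points.

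*Conversely,* 60% adherence among users in both arms with uptake of 20% v 30% gives a user difference of 0, but 12 v 18 adherent users per 100 identified.

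**Effect of analysing everyone.** With equal uptake u, a 15-point difference confined to users becomes 15 × u over all identified patients:

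- u = 16%: 2.4 points
- u = 30%: 4.5 points
- u = 50%: 7.5 points

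All three lie inside ±10 points, the margin stated for Aim 2 only.

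**The case against.** A reader might infer that adherence can only ever be scored in testers. The documents do not support that. The time anchor includes last services contact, non-testers report screening at 12 months, and record tracking is planned for patients identified by the algorithms. The sentence on electronic-record adherence carries no explicit restriction to testers. The defect is an unspecified analysis, not missing capability. Nor do the documents say that non-testers receive no advice: pre-test counselling includes risk assessment, and letters for negative results rest on family history, which is known for every flagged patient. The front page also points to a separately published full protocol, not available here, which may define adherence further.

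A reader might also infer that the models are known to select different patients. That is an inference, though a well-founded one. It rests on the different routes and on the Background, which cites a randomised trial where the effect of delivery mode differed by race and minority women assigned to telephone counselling were least likely to complete testing. If most users would engage under either model, the bias may be small.

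The planned models adjust for patient-level covariates, and a large uptake gap would be visible in Aim 2. Both are true. Adjustment covers only measured differences, and the equal-uptake cases above need no uptake gap.

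Finally, adherence among people given a recommendation is a legitimate question. It is, but it does not by itself answer the stated one about the effects of randomised models. Planned record tracking does not close the gap either. No adherence endpoint is defined for all identified patients, and the comparison described in Research Procedures 5 is between questionnaire returners and similar cohorts.

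**Conclusion.** The point holds in this form: as defined, the Aim 3 adherence comparison is conditional on engagement after randomisation, which the delivery model influences, and the plan commits to no comparison of all identified patients by allocated clinic. A user-only result cannot on its own support equivalence of the models.

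The size and direction are unknown. Under the assumed values the distortion runs from about 2 points (90% overlap of users, 20-point gap) to 11.5 points (uptake 16% v 26%), and a true 15-point deficit can be masked completely. These figures rest on assumed overlap, uptake and adherence; none is a prediction for this trial.

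A reader might go further and infer that every untested patient should simply count as non-adherent. The documents do not support that as the sole endpoint. It would largely restate Aim 2, pull differences toward equivalence, and score as failures any untested patients who had appropriate screening based on family history.

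**What to change.** 1. Add an Aim 3 analysis of all eligible patients identified by the algorithms, by allocated clinic. Set time zero at identification or outreach. Use an electronic-record outcome that can be scored for everyone, namely completion of relevant screening or management within the window, and do not score untested patients automatically as non-adherent. Research Procedures 4 limits recording to care related to genetic services, so state that screening is abstracted whether or not the patient had services contact. A composite of recommendation on record and acted on may be shown as a supplementary yield per identified patient.
2. Keep adherence among testers or service users, labelled conditional and non-randomised, and draw no claim of equivalence between the models from it alone.
3. Do not reuse the Aim 2 margin of ±0.10 for the all-patients comparison. Justify a margin on that scale, because dilution favours equivalence.
4. Reconcile Research Procedures 4 with the authorisation-waiver request, which describes tracking of, and record access for, patients who use genetic services.

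The cost is some extra definition, abstraction and analysis, using records already planned for tracking and needing no new patient contact. The all-patients estimate is diluted and partly reflects uptake, which is why the conditional result stays alongside it. The continuing review submitted in January 2024 reports analysis of the primary outcomes under way. The addition should therefore be dated, and called post hoc if adherence by arm had already been seen.
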